A. The **Primary Objectives** are to demonstrate that Veterans with chronic SCI of \geq six months duration who are medically stable and are wheelchair users for indoor and outdoor mobility as their standard of care (SOC) plus use of an exoskeletal-assisted walking device in their home and community environments will have clinically meaningful net improvements in the MCS/VR-36 and in patient-reported outcomes for the SCI-QOL bladder, bowel, and pain item banks compared with those who use only SOC for home and community mobility. The primary outcomes to be assessed will be the MCS value and the sum T-score of the SCI-QOL bladder management difficulties, bowel management difficulties and pain interference item banks.

B. The **Major Secondary Objective** is to demonstrate that participants who use the exoskeleton in addition to SOC will have at least a 1.0 kg loss in total body fat mass by the end of the four-month Intervention phase.

C. The **Secondary Objectives** are to demonstrate that participants who use the exoskeleton in addition to SOC will have greater net improvements than the participants who receive only SOC on the following outcomes:

1. Global Impression of Change Scale (Participant- and Companion-rated).

2. Disturbed sleep as measured by the T-score of the Patient Reported Outcomes Measurement Information System (PROMIS) Sleep Disturbance (short form).
3. Self-reported methods and measures of bowel function for:
 - a. frequency of bowel evacuation episodes, time per episode, number of self-reported “natural” bowel movements, the amount of bowel evacuation medications used (e.g., laxatives and/or stool softeners), frequency of enemas used, frequency of digital stimulation needed per week, stool consistency (by the Bristol Stool Scale), and frequency of bowel incontinence/accident episodes;
4. Sum T-score of the SCI Functional Index (SCI-FI) physical function short forms (basic mobility, self-care, fine motor, ambulation, wheelchair mobility, and assistive technology);
5. Sum T-scores of the SCI-QOL Emotional domain (Separate T-scores for: 1) anxiety, depression, grief-loss, trauma, and stigma item banks, and 2) positive affect and well-being, self-evaluation, and resilience item banks) (short form);
6. Sum T-score of the SCI-QOL Social Participation domain (ability to participate in social roles and activities, satisfaction with social roles and activities, and independence) (short form);

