The DMC will be responsible for review of the SAEs and AEs for each site and across the study as a whole. The DMC will make all decisions for stopping the study based on safety concerns, should any present. Early analyses before the study is completed may result in stopping of the study. For example, if it is statistically demonstrated that the results for either efficacy or futility to date could not be changed with further enrollment, the study may be stopped. When repeated significance tests are performed on accumulating data as part of a routine monitoring function, the overall type-I error rate is inflated and the probability of a false positive finding is also increased. A number of methods have been developed to provide guidance on study termination rules based on multiple looks at the primary outcome measures for the review committees while keeping the overall type-I error rate maintained at 5%. For this study, the O'Brien-Fleming method for alpha spending and rejection/acceptance boundaries will be suggested for Type-I error rate control (see Statistical Analysis Plan (SAP – Section XIII) for further details) but the DMC will make the final decision on the type of stopping rule that will be used for the study.

XII. QUALITY ASSURANCE PROCEDURES

Centralized and on-site reviews and monitoring of clinical site practices will be conducted at several levels. The National Coordinator will visit each site two times per year during the enrollment years to monitor the EAW Training, patient safety, and compliance with the study protocol. The Co-National Coordinator will visit each site one time annually during the enrollment years to monitor standardization of the QOL assessments and protocol compliance. Participant's medical records will be made available to the CSP Site visitors as a requirement for participation in this study.

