Sample size/power calculation for the Primary Outcome (2) SCI-QOL for Bladder, Bowel and Pain: An improvement of 10% in the sum T-score of the patient-reported outcomes from the combined SCI-QOL item banks for bladder management difficulties, bowel management difficulties and pain interference is clinically significant. As such, it is hypothesized that 42% of the Intervention group compared with 10% of the Control group will demonstrate a clinically significant change of 10% improvement from baseline to the end of the intervention phase on the sum T-score in the combined SCI-QOL item banks for bladder management difficulties, bowel management difficulties and pain interference. (Table 7).

Sample size/power calculation for the Major Secondary Outcome for Total Body Fat Mass: Patients with a new SCI can be expected to gain an average of 6.0 ± 8.9 kg of fat mass in the first 14 months after injury (manuscript in preparation from our Center). This gain in fat mass appears to continue throughout the duration of their life after SCI. As demonstrated in the preliminary data, an intervention that supports a 1.0 kg (2.2 lb.) loss of fat mass is a substantial amount of fat mass to lose in three months for a person with SCI. Very few interventions have demonstrated changes in body composition of this magnitude in the SCI population. It is expected that 35% of the Intervention group compared with 10% of the Control group will maintain total body fat mass loss during the home/community use phase of the intervention.

Assuming the proportion in the control group achieving a clinically meaningful change to be 10% (or 0.100) for all three outcome measures, and estimating the attrition rate at 15%, the sample sizes range from a low of 71 per group (95% power) for the SCI-QOL PMH outcome to a high of 79 per group (80% power) for the MCS/VR-36 group. As a note about Table 7, to adjust for multiple outcome measures, a significance level of 0.025 was used in the sample size calculations for the co-primaries (MCS/VR-36 and SCI-QOL) and also for the major secondary outcome measure (Total Body Fat Mass). Based on the sample size and power calculations in Table 7, the study will enroll a total sample size of 160 participants, 80 per group.

Table 7: Sample Size/Power Calculations			
Two group continuity corrected χ^2 test of equal proportions (odds ratio = 1) (equal n's)	MCS/VR-36	SCI-QOL (PMH)	Total Body Fat Mass
Test significance level, α	0.025	0.025	0.025

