group will have a clinically meaningful change in the outcome measures for sample size/power calculations. Ten percent is thought to be a conservative estimate as there is no reason to expect the control group to have clinically meaningful changes in quality of life measures or in total body fat mass while continuing to receive SOC for their spinal cord injury. However, as a means of verifying the control proportion of 10% (or 0.100), the proportion of participants considered successful in the control group for all three outcomes and 95% confidence intervals for the proportions will be reviewed upon the completion of the feasibility phase. Based on the extensive experience with this population it is highly unlikely that the assumed success rates in the control group (SOC) will be any higher than the assumed 10%.

At the completion of the feasibility phase, the study will be moved to a continuation phase where the remaining sites (9 remaining sites) will be activated and the remaining participants will be recruited.

D. Baseline Comparability

Baseline comparability between the treatment groups will be evaluated with respect to such variables as demographics (e.g., age, gender, and race) and baseline values of outcome measures (MCS/VR-36, SCI-QOL, total body fat mass, etc.). Chi-square and analysis of variance techniques, as appropriate, will be used to determine any differences in distribution of the variables across the treatment groups. Any variable that appears to be different between the groups ($p < 0.10$) will be considered as a potential covariate in statistical analyses.

E. General Outcome Analysis Guidelines

All statistical tests will be 2-sided. The two primary and major secondary outcome measures will be tested at a 0.025 level of significance. Because of the large number of secondary outcomes to be analyzed, all other secondary outcomes will be tested at a significance level of 0.01 to maintain control over Type I error. SAS 9.4 will be used to conduct all the statistical analyses. A variety of analytic methods will be used for the primary endpoints, secondary endpoints and other analyses.

F. Analysis of Primary and Major Secondary Outcome Measures

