The primary analysis will be based on an intent-to-treat (ITT) model. All participants who are randomized will be included for both groups, whether they are study completers (participants who complete the study through the four-month intervention phase) or early terminators (drop-outs). In order to test the hypotheses for the primary and major secondary outcome measures, each randomized participant will be deemed a success or failure at attaining: 1) ≥ 4.0 point improvement in the MCS of the VR-36, 2) $\geq 10\%$ improvement in the SCI-QOL bladder management difficulties, bowel management difficulties and pain interference sum T score, and

3) ≥ 1 kg. total body fat mass loss. For each of the outcomes, the proportion of participants successful at achieving a clinically significant improvement will be compared between the two groups (Intervention vs. Control) using a chi-square analysis. These will constitute the primary and major secondary efficacy analyses. Participants who drop out will be treated as failures. As such, by design, there will be no missing data: participants either meet the outcome criteria (successes), do not meet these criteria (failures) or they drop out (also failures).

G. Secondary Analyses

In addition to the primary analysis, several secondary analyses will be performed and are described below.

1. Analyses will be performed that include only those participants who complete the study (excluding drop-outs):
 - a) Chi-square analyses of the primary and major secondary outcome measures (proportion of successes) will be repeated for only those participants who complete the 4-month intervention phase.
 - b) Analyses of the MCS/VR-36, SCI-QOL, total body fat mass loss, Global Impression of Change and other secondary outcome measures will include comparisons of the mean difference scores (change from baseline to the end of the intervention phase) of these outcome variables using t-tests.

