For the DMC to make its recommendation for continuation of the study, it will be necessary for them to see the analysis of the primary and major secondary outcome measures every time they are provided a report of study progress and it is possible to calculate these measures. Periodic monitoring of interim results can significantly affect the probability of making an incorrect decision (Type-I error rate). One interim look at the primary outcome measures (in addition to the final “look” at study’s end) will be proposed to the DMC for making the recommendation about whether or not to continue the trial or to stop for early efficacy. It is proposed that the one look occur when 80 (50%) patients have completed participation in the study. The O’Brien-Fleming method for alpha spending and rejection/acceptance boundaries will be suggested for Type-I error rate control. The O’Brien-Fleming boundaries for rejection (α) and acceptance (β) as well as the Type-I error rates for the two looks are given in Tables 15 and 16 for the MCS/VR-36 and SCI-QOL/PMH outcomes, respectively. The boundaries are presented graphically in Figures 10 and 11 for the two primary outcome measures.

Table 15. CS #2003: Two-sided O’Brien-Fleming Boundaries for Rejection (α) and Acceptance (β) – MCS/VR-36

Interim Look (Stage)	No. of Randomized Participants	Std. z (Rejection)		Std. z (Acceptance)		Type-I error
		Lower	Upper	Lower	Upper	
1	80	-3.12376	3.12376	-0.88945	0.88945	0.00089
2	160	-2.20883	2.20883	-2.20883	2.20883	0.01250

Figure 10. CS #2003 Combined Boundary Plot for MCS/VR-36

[figure not shown]
[figure not shown]

Table 16. CS #2003: Two-sided O’Brien-Fleming Boundaries for Rejection (α) and Acceptance (β) – SCI-QOL Physical Medical Health (PMH) domain

Interim Look (Stage)	No. of Randomized Participants	Std. z (Rejection)		Std. z (Acceptance)		Type-I error
		Lower	Upper	Lower	Upper	
1	80	-3.16956	3.16956	-0.40071	0.40071	0.00076
2	160	-2.24122	2.24122	-2.24122	2.24122	0.01250

Figure 11. CS #2003 Combined Boundary Plot for SCI-QOL Physical Medical Health (PMH) Domain

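### Testing the two primaries at a fixed 0.025 each is valid, but Holm keeps the same 5% error and gives MCS/VR-36 more power; the either-or-both rule should be stated

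*Combined protocol and SAP*

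**What the plan says.** - **Level.** XIII.E: "The two primary and major secondary outcome measures will be tested at a 0.025 level of significance". XIII.B gives the reason: "to adjust for multiple outcome measures, a significance level of 0.025 was used in the sample size calculations for the co-primaries". All tests are two-sided.
- **Structure.** Section II.D lists the primary hypotheses separately as a and b. Table 7 gives each its own level and power. Tables 15 and 16 give each its own O'Brien-Fleming limits.
- **Objective.** Section II.A joins the two with a conjunction: intervention participants "will have clinically meaningful net improvements in the MCS/VR-36 and in patient-reported outcomes for the SCI-QOL bladder, bowel, and pain item banks" compared with controls. No sentence says whether one positive primary is enough.
- **Analysis.** XIII.F: the success proportions "will be compared between the two groups (Intervention vs. Control) using a chi-square analysis". It does not mention the continuity correction that Table 7 uses. On missing outcomes: "Participants who drop out will be treated as failures".
- **Interim.** XIII.I proposes "One interim look at the primary outcome measures" to the DMC, once 80 participants (50%) have completed. XI.J speaks of "keeping the overall type-I error rate maintained at 5" per cent when primary outcome measures are looked at repeatedly, and leaves the stopping rule to the DMC.

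The plan contains no step-down or alpha-recycling rule.

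**The concern.** Halving alpha protects a claim based on either primary. If that is the rule, a fixed split gives up power once one primary is significant: Holm then allows the other to be tested at 0.05 with no loss of error control. If both primaries were required instead, no split would be needed.

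The loss falls on MCS/VR-36, which has the lowest planned power of the three sized outcomes (80%). SCI-QOL is planned at 95%, so on the plan's own assumptions the condition that releases 0.05 for MCS would usually be met.

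**Working it through.** **Inputs** (XIII.B, Table 7): two-sided α = 0.025; control rate p1 = 0.100; intervention rate p2 = 0.333 (MCS), 0.420 (SCI-QOL), 0.350 (fat mass); attrition 15%; 80 per group enrolled. The documents give no correlation between the two primaries; independence is assumed and then varied.

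**1. Reproduce Table 7.** With d = p2 − p1 and p̄ = (p1 + p2)/2,

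n′ = [z(1−α/2)·√(2p̄(1−p̄)) + z(power)·√(p1(1−p1) + p2(1−p2))]² / d²

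n = (n′/4)·[1 + √(1 + 4/(n′d))]²

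MCS: n′ = (2.2414 × 0.5825 + 0.8416 × 0.5587)² / 0.233² = 58.1, so n = 66.4, rounded up to 67; 67/0.85 gives 79. SCI-QOL gives 60 (71) and fat mass 66 (78). All match.

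**2. Power at 67 per group.** Undoing the correction for MCS: n′ = (√67 − 1/(0.233·√67))² = 58.69.

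- MCS at 0.025: Φ[(0.233·√58.69 − 2.2414 × 0.5825)/0.5587] = 0.80463
- MCS at 0.05 (1.960 in place of 2.2414): 0.87528
- SCI-QOL in the same way: 0.9723 at 0.025 and 0.9867 at 0.05

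**3. MCS power under Holm, independent outcomes.** MCS is rejected at 0.025, or at 0.05 once SCI-QOL is rejected at 0.025:

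0.80463 + P(SCI-QOL rejected at 0.025) × (0.87528 − 0.80463)

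| SCI-QOL intervention rate | P(SCI-QOL rejected at 0.025) | MCS, fixed split | MCS, Holm |
|---|---|---|---|
| 42% (planned) | 0.9723 | 80.5% | 87.3% |
| 35% | 0.8567 | 80.5% | 86.5% |
| 30% | 0.6740 | 80.5% | 85.2% |
| 20% | 0.1919 | 80.5% | 81.8% |
| 10% (no effect) | at most about 0.025 | 80.5% | about 80.6% |

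With an assumed correlation of 0.5, the Holm figures are 87.2% at 42%, 85.7% at 35% and 83.8% at 30%. To reach 87.3% with the fixed split would take 78 per group, or 92 with attrition (78/0.85), against 79: 2 × (92 − 79) = 26 more participants.

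**4. Power for both primaries (SCI-QOL 42%).**

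- Fixed split: 0.8046 × 0.9723 = 78.2%
- Holm: 0.8753 × 0.9867 − (0.8753 − 0.8046) × (0.9867 − 0.9723) = 86.3%
- 0.05 each, if both are required: 0.8753 × 0.9867 = 86.4%

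**5. Power for at least one primary.** 1 − (1 − 0.8046)(1 − 0.9723) = 99.5% for the fixed split and for Holm alike, because Holm's first step is the fixed split.

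**6. Error over the two primaries.** Fixed split: at most 0.05 (1 − 0.975² = 0.0494 if independent). Holm: at most 0.05. Testing each at 0.05 is safe only if both are required; if either sufficed it would give 1 − 0.95² = 0.0975.

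**7. Dropouts as failures** (exact, 80 per group, success rates × 0.85, SCI-QOL 42%). MCS goes from 81.0% to 87.6% with the continuity correction, and from 86.5% to 91.5% without it.

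**8. With the interim look** (2 million simulated trials, look at half the information, drifts matched to step 2, independent outcomes).

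- Efficacy-only limits, follow-up continuing for the second primary: about 80.3% to 86.9%. The limits are 3.183/2.250 at 0.025 and 2.797/1.977 at 0.05. Simulated familywise error is 0.049 with both nulls true and 0.050 with one.
- Table 15 and 16 limits with interim acceptance final: about 78.4% to 82.7%. MCS has a 9.5% chance of interim acceptance at its planned effect.
- SCI-QOL crosses at the look in about 40% of trials. If the trial then stops, MCS power is about 54% with the fixed split and 63% with Holm.

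**The case against.** **The split is a legitimate choice.** It controls error, needs one set of limits per outcome and gives two plain 97.5% intervals. This stands: the point is about efficiency and clarity. A reader might infer that the error over the two primaries is uncontrolled, and it is not. Tables 15 and 16 each total 0.0250 when acceptance is binding.

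**If either primary suffices, the power that matters is for at least one, and Holm leaves it unchanged.** Correct. The gain is for MCS by itself and for showing both. It is still worth having, because the plan sizes and reports each primary as a hypothesis of its own.

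**A split result is not without status.** A reader might infer that one positive and one negative primary would be uninterpretable. The separate hypotheses, levels, tests and limits point to either sufficing, and the conjunction in II.A can be read as a list of objectives. What remains is that the rule has to be inferred.

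**The headline gain is the favourable case.** The 42% rests on 5 of 12 pilot participants. The gain shrinks to 1.3 points at 20% and to about 4 points if interim acceptance is final. If the chi-square is uncorrected, MCS already has 86.5%. The interim figures also depend on follow-up continuing. All of this stands, and the gain should be quoted as a range.

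**Fat mass.** Three tests at 0.025 have a nominal bound of 7.5%, so a reader might infer a broken promise. The plan nowhere promises 5% over three outcomes; XI.J speaks of the primary outcome measures, in a general account of sequential methods, and XIII.I gives limits for the two primaries only. For null rates of 10–30% with independent tests, the exact three-test error is 3.5–4.8% corrected and 6.4–7.3% uncorrected. A clarifying sentence is optional.

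**Conclusion.** The point holds as a low-cost improvement to a valid plan. At the same 5% over the two primaries, Holm is never less powerful than the fixed split. Under the plan's assumptions it adds about 7 points of MCS power and about 8 points for both primaries. The MCS gain is about 5 points if SCI-QOL responds at 30%, about 1 point at 20% and almost nothing with no SCI-QOL effect. With the interim look it is between about 4 points (acceptance final) and 6.6 points (efficacy-only, follow-up continuing). With an uncorrected chi-square it is 5 points, from a higher base.

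The figures rest on independent primaries, though a correlation of 0.5 changes them little, and on Table 7's response rates except where varied.

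**What to change.** 1. **XIII.E.** State that either primary suffices, and test the two by Holm: 0.025 each and, once one is rejected, the other at 0.05. If the sponsor instead requires both, test each at 0.05.
2. **XIII.I, as a proposal to the DMC.** Under Holm, give O'Brien-Fleming limits at both levels for one look at 50%: efficacy-only 3.183/2.250 (0.025) and 2.797/1.977 (0.05). Say whether follow-up continues for the second primary after the first crosses. If acceptance limits are kept, say whether they are final and, if so, recompute both sets; ignoring them would put the error of Tables 15 and 16 at 0.0279 and 0.0256.
3. **Optional.** Say that fat mass at 0.025 lies outside the 5% family (XIII.B and E), and whether the chi-square is continuity-corrected (XIII.F).

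**Cost.** SAP text and a second set of limits; no added participants. Simultaneous confidence intervals become less simple than two 97.5% intervals. The change must be made by people who have not seen outcomes by group. That needs care: the study biostatistician sits on the Executive Committee (XI.B) and also heads the coordinating-center team (X.A) that prepares DMC reports by treatment group (XIII.I). The protocol version is dated July 2021, after the planned end of enrollment in Table 5.

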Duration of Participant Intake (Study Duration) The CS #2003 study duration is projected to be a total of seven years: The initial six sites will have a start-up year, followed by participant enrollment/data collection during years 1-4, and continued data collection/closeout during year 5, for a total of six years. The next four sites will begin the start-up year one year after the first six sites and follow the same enrollment, data collection and closeout schedule over the next five years. The next five sites will begin start-up one year after the four sites and follow the same enrollment, data collection and closeout schedule. All fifteen sites will be closed out after six years, and there is an additional year for the Coordinating Center and Chairperson's Office to complete data analysis and manuscript writing, thus the study total time is seven years. Participants in both groups will be asked to commit 33 weeks to this study. Participants in the Control arm will be offered an additional 8 weeks to receive EAW training in the medical centers, without outcome data being collected.

Treatment (follow-up) The intervention being tested is four months of home and/or community use of a powered exoskeleton.

Definition of Participant Samples (Study Population) One-hundred sixty male or female Veterans or military members with chronic SCI, \geq six months duration, \geq 18 years of age, functional use of their hands, medically stable, and wheelchair users for indoor and outdoor mobility, will be eligible for screening. All potential participants will be Veterans or military members with SCI. Study participants will generally be outpatients with the exception of those inpatients who meet the eligibility criteria, and who are approved by the Site Investigator (e.g., some inpatients may have been admitted for a wheelchair fitting or another non-medical reason). Non-veterans with SCI will not be eligible.

Treatment Arms All participants will receive four months of treatment, randomized into two arms: SOC plus EAW or SOC only.

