closeout at the study sites. During Year 7, data analyses and manuscript writing will be performed. A detailed description may be found in the “Study Timeline” (Table 5).

Participants in the Intervention group will require eight to nine months to complete the study. Participants in the Control group will require seven to nine months for study completion. The extra time is for the optional Control EAW in-hospital training sessions after the study is completed. This amount of time breaks out as follows. Once consented, potential participants will need one week for the screening evaluations, one week for the baseline outcome evaluations, and two weeks for the device fitting and five-session basic skills training and skills test. The Intervention group will go through a three-month Training phase, which includes the additional 25±5-sessions of supervised EAW training with their companion. After randomization, the Control group will participate in a two-month Orientation phase. The Intervention phase will require four months for both groups. The post evaluations will require one week. Those in the Control group will have the opportunity to participate in an additional two-month optional EAW outpatient training without data collection. A detailed description may be found in the “Training and Testing Schedule” (Table 6).

Table 5. Study Timeline	Funding notification (8/12/2015) 6-week Pre Start-up (no study costs)	Start-up				Y1				Y2				Y3				Y4				Y5				Y6						
		Enrollment & Participant Data Collection (160 Participants to be enrolled by end of Q4 Y4)																				Study Closeout				Data Analyses and Manuscript Writing						
		FY16				FY17				FY18				FY19				FY20				FY21				FY22						
		Start-up Year (6 Sites)				Enrollment Year 1 (6 Sites) Start-up year (4 Sites)				Enrollment Year 2 (6 Sites) Enrollment Year 1 (4 Sites)				Enrollment Year 3 (6 Sites) Enrollment Year 2 (4 Sites) Start-up & Enrollment Year 1 (5 Sites)				Enrollment Year 4 (6 Sites) Enrollment Year 3 (4 Sites) Enrollment Year 2 (5 Sites)				Participant Carry-over and Study Close-out (All 15 sites)				Study analyses and write-up						
		Q1	Q2	Q3	Q4	Q1	Q2	Q3	Q4	Q1	Q2	Q3	Q4	Q1	Q2	Q3	Q4	Q1	Q2	Q3	Q4	Q1	Q2	Q3	Q4	Q1	Q2	Q3	Q4	Q1	Q2	Q3
Administration start up	x	x																														
Chair's Office CIRB	x	x																														
CSPCRPCC IDE to FDA	x	x																														
Chair/Sites' PDs	x	x																														

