1 or 2 sided test?	2	2	2
Control proportion, π_1	0.100	0.100	0.100
Intervention proportion, π_2	0.333	0.420	0.350
Odds ratio, $\psi = \pi_2(1 - \pi_1) / [\pi_1(1 - \pi_2)]$	4.493	6.517	4.846
Power (%)	80	95	85
n per group	67	60	66
n per group with 15% attrition	79	71	78

C. Feasibility Phase

In order to confirm the hypothesized control proportion for the two primary and major secondary outcomes, to determine the feasibility of recruiting participants at each site, and to assess other operational aspects of the study, a feasibility phase has been built into this study. The planned duration of the feasibility phase of the study is one year. Six out of fifteen planned sites (including three sites that are designated CSP NODES) will be brought up in the first year.

During the feasibility phase, several site start-up activities and operational aspects of the study will be examined. These activities will include the hiring of site personnel (including classification of position descriptions, position announcements and recruitment), the processes for procuring and distributing the ReWalk and iDXA devices to the sites, the methods by which site staff are trained on the use of the devices and on data collection and management activities, the number of sessions needed for participants in the intervention group to pass the Advanced Skills Test, the practicality of Veterans or members of the military with SCI to find motivated and eligible walking companions, and attrition (drop-out) rates. The lessons learned during this phase will be implemented during activation of the remaining participating sites.

Recruitment rates at the six active sites will be closely monitored during this phase. The initial six sites are expected to enroll a total of 48 participants by the end of the first year. The actual recruitment experience of the six sites in the first year will be used to revise the projected recruitment rate for the remainder of the study and may lead to a lengthening or shortening of the total recruitment period, as appropriate.

Besides the verification of the assumed recruitment rate and other site start-up activities, the feasibility phase also provides an opportunity to assess the assumed success rates in the control (SOC) group. As stated above in section II, we have hypothesized that 10% (0.100) of the control

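### Does the one-year feasibility review need a decision rule because it will hold too few controls to confirm the 10% control rate?

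*Combined protocol and SAP*

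**What the plan says.** Section XIII.C opens the feasibility phase with this aim, among others: "In order to confirm the hypothesized control proportion for the two primary and major secondary outcomes". It adds: "The planned duration of the feasibility phase of the study is one year", and "The initial six sites are expected to enroll a total of 48 participants by the end of the first year". For the control rate, the proportion successful on each of the three outcomes is tabulated and "95% confidence intervals for the proportions will be reviewed upon the completion of the feasibility phase". The 10% itself is supported by judgement: the section sees no reason for controls to improve and appeals to experience with this population. The pilot results for the two primary outcomes (section I.C) are single-group, before and after.

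On timing, the Executive Summary says "Participants in both groups will be asked to commit 33 weeks to this study". Section III.D says "After randomization, the Control group will participate in a two-month Orientation phase", while Table 6 gives Orientation/Training weeks 5 to 16 and the post-intervention evaluation week 33.

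On consequences, XIII.C says "At the completion of the feasibility phase, the study will be moved to a continuation phase", with no condition attached. Recruitment experience, by contrast, "may lead to a lengthening or shortening of the total recruitment period, as appropriate". Section XIII.I then routes the feasibility data, with the control success rates named, to the DMC for recommendations. Section XI.C lets the DMC recommend that the study continue, be modified or be stopped.

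**The concern.** A check described as confirming an assumption should be able to contradict it. This one will rest on about ten people, and XIII.C names no number of control successes that would trigger anything. The control rate enters every column of Table 7, and the MCS outcome, which needs the largest sample (79 per group), is sensitive to it. If the true rate were 15% or 20% and the intervention rate stayed at 33.3%, the trial would be short of power and the review would probably not show it. A later change of sample size would also come from a committee that already sees the comparison between arms. That is a reason to prefer a rule written in advance.

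**Working it through.** **1. Table 7 reproduces.** Inputs: two-sided alpha 0.025, control 0.100, MCS intervention 0.333, continuity-corrected chi-square. With d = p2 − p1 and p̄ the mean of the two rates, the corrected test at n per group behaves like an uncorrected one at n′ = n − 2/d + 1/(n·d²). Power = Φ{[d√n′ − 2.2414·√(2p̄(1−p̄))] / √(p1(1−p1) + p2(1−p2))}.

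For n = 67: d = 0.233, n′ = 58.7, power = Φ[(1.785 − 1.306)/0.559] = 80.5%. Solving for n gives 67, 60 and 66 for the three outcomes. Dividing by 0.85 gives 79, 71 and 78, as printed.

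**2. Controls with an outcome at one year.** Of 48 enrolled, 24 are controls. In Table 6 the outcome falls 33 − 4 = 29 weeks after randomisation; with a two-month Orientation it falls about 25 weeks after. With even accrual:

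- 24 × (52 − 29)/52 = 10.6
- 24 × (52 − 25)/52 = 12.5
- randomisation starting only in week 5: 24 × 19/48 = 9.5 and 24 × 23/48 = 11.5

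That is about 9 to 12. The two Orientation lengths differ, but the conclusion is the same under either.

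**3. What the interval can show.** With no successes the exact upper limit is 1 − 0.025^(1/n).

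| Controls | Upper limit, 0 successes | Successes needed for lower limit above 10% | Chance interval still includes 10% if true rate is 15% / 20% / 25% |
|---|---|---|---|
| 9 | 33.6% | 4 | 97 / 91 / 83% |
| 12 | 26.5% | 5 | 98 / 93 / 84% |
| 24 | 14.2% | 7 | 94 / 81 / 61% |
| 40 | 8.8% | 9 | 86 / 59 / 30% |

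With no successes, 36 controls are needed to bring the upper limit to 10% or below. The one-year review can therefore flag only a gross error. At a true rate of 30% the lower limit exceeds 10% in 27% to 43% of cases for n = 9 to 12.

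**4. What the control rate does to power** (80 per group, alpha 0.025, corrected / uncorrected):

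| Control rate | MCS, intervention 33.3% | MCS, difference held at 23.3 points | SCI-QOL, intervention 42% |
|---|---|---|---|
| 10% | 88 / 92% | 88 / 92% | 99 / 99.5% |
| 15% | 61 / 68% | 83 / 87% | 92 / 95% |
| 20% | 30 / 37% | 78 / 83% | 73 / 78.5% |

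The documents do not say whether the intervention rate or the difference would stay fixed.

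**5. What a rule would buy.** Take an illustrative rule at the proposed look at 80 completers (about 40 controls): extend to 120 per group if at least 6 of 40 controls succeed. In 400,000 simulated trials per setting, using Table 15's rejection limits (3.12376 and 2.20883), MCS power at 15% versus 33.3% is:

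| | Without rule | With rule |
|---|---|---|
| Acceptance limit ignored, corrected / uncorrected | 64 / 70% | 79 / 84% |
| Acceptance limit 0.88945 applied at the look | 59 / 67% | 67 / 75% |

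If the Table 15 boundaries stay as printed, the second row applies. The gain is then about 8 points and power stays below 80%. The rule fires in 21% of trials when 10% is true, and misses 100 − 57 = 43% when the truth is 15%.

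**6. When the look would come.** Section XIII.H projects 48 participants in the first recruitment year and 80 in the second. The 80th is randomised at week 52 + (32/80) × 52 = 72.8 and finishes 25 to 29 weeks later, at week 98 to 102. By then 48 + 80 × (97.8 − 52)/52 = 118 to 48 + 80 × (101.8 − 52)/52 = 125 of the 160 are randomised.

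**The case for a change.** The strongest case for a change is that the plan gives the review a job it cannot do, on an assumption that may be optimistic. A responder cut-off counts individual fluctuation as well as true improvement. The pilot MCS change had an SD of 17.02. If control changes were normal with mean zero, a 10% rate of gains of 4 points or more would imply an SD of only 4/1.28, about 3. A report could also cite the review as confirmation that ten or so controls cannot give.

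Part of this stands. The verbs in XIII.C are stronger than the data will bear, and 10% rests on judgement. The pilot SD comes from 11 people and includes any treatment effect, so it is only indicative, but it is a fair reason to read the MCS power with caution.

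The claim that nothing is tied to the result does not stand. XIII.I presents the control rates to the DMC, which also receives outcomes by arm in its six-monthly reports. What is missing is a numerical threshold, and with 9 to 12 controls any threshold would be unreliable. A rule at 80 completers has better data but comes late, is modest in effect, and hangs on a look that is itself only a proposal to the DMC (sections XI.J and XIII.I). It may also be too late: this version is dated July 2021, Table 5 ended enrolment in FY20, and Table 21 shows 423 screened by March 2020 against at least 60 expected at each of 15 sites (900).

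**Conclusion.** No change follows. The review will be weak: about 9 to 12 controls, and an upper limit of 26% to 34% even with no successes. This assumes that the feasibility year is the first recruitment year and that accrual is even; a slower start gives fewer controls. But the result is an interval whose width shows that weakness, and it goes to a committee empowered to recommend changes. Analysts will report the number of controls behind a proportion as a matter of course, so softer wording would leave every analysis and conclusion as it is.

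The substantive alternative, sample-size re-estimation on the control rate, is a design option and not the repair of an error. At the plan's own 10%, 80 per group gives 88% MCS power with correction, above the stated 80%. The rule examined could cost up to 80 more participants for about 8 points of MCS power at a 15% control rate with Table 15 intact, and 15 points only if the acceptance limit is ignored. Keeping the sample size fixed and leaving the judgement to the DMC is a fair trade-off. The shortfall in MCS power at 15% to 20% is real if the intervention rate stays at 33.3% (61% to 30%, corrected) and small if the difference holds (83% to 78%).
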